**Table 3 Schedule of Procedures/Assessments in Study FYU-981-J086-301**

Phase	Screening	Treatment I			Treatment II					ET a	Unscheduled o
Visit	1	2	3	4	5	6	7	8			
Week	-4	0 b	4 c	8	12 d	16	20	24 e			
Day	-28	0	28	56	84	112	140	168			
Possible Study Day(s) Given Window	-28 to -4	0	23 to 33	51 to 61	77 to 91	105 to 119	133 to 147	161 to 175			
Procedures/Assessments											
Demography	X										
Informed consent/assent	X										
Inclusion/exclusion criteria											
Medical history	X										
Alcohol consumption status	X										
Prior and concomitant medication(s)									X	X	
Urinary tract management f	X	X	X	X	X	X	X	X	X	X	
Adverse events									X	X	
Gouty arthritis									X	X	
Randomization		X									
Study drug		Day 1 									
Study drug compliance			X	X	X	X	X	X	X	X	
Dispense study drug			X	X	X	X	X				X
Retrieve unused study drug				X	X	X	X	X	X	X	
Physical examination g	X				X			X	X	X	
Vital signs h and weight	X	X	X	X	X	X	X	X	X	X	
Height i	X										

**Table 3 Schedule of Procedures/Assessments in Study FYU-981-J086-301**

Phase	Screening	Treatment I		Treatment II					ET a	Unscheduled o
Visit	1	2	3	4	5	6	7	8		
Week	-4	0 b	4 c	8	12 d	16	20	24 e		
Day	-28	0	28	56	84	112	140	168		
Possible Study Day(s) Given Window	-28 to -4	0	23 to 33	51 to 61	77 to 91	105 to 119	133 to 147	161 to 175		
Procedures/Assessments										
Clinical laboratory tests j	X		X	X	X	X	X	X	X	
Viral screening k	X									
Serum uric acid level l	X		X	X	X	X	X	X	X	
Serum β-hCG (or hCG) test m	X							X	X	
Classification of hyperuricemia p	X									
eGFR	X									
12-lead ECG n	X				X			X	X	X
Abdominal ultrasound /abdominal radiography	X							X	X	

X: required done.

$\beta$ -hCG = beta-human chorionic gonadotropin (or hCG = human chorionic gonadotropin); CRF = case report form; ECG = electrocardiogram; eGFR = estimated glomerular filtration rate; ET = early termination; HBsAg = hepatitis B surface antigen; HCV = hepatitis C virus; HIV = human immunodeficiency virus; SUA = serum uric acid.

- a: These assessments will be conducted for subjects who discontinued the study early for any reason after Visit 2.
- b: Subjects who have developed gouty arthritis attack after the randomization day and before taking the first study drug are not to receive the study drug, and the subjects are to be discontinued from the study.
- c: Subjects who have developed gouty arthritis that has not disappeared by Week 4, are to continue to take the current investigational product without increasing dose for up to 1 week after the specified visit date (ie, up to Day 35) until the event disappears, and following the resolution of event, the study drug with increasing dose is to be dispensed at an Unscheduled Visit (ie, before or on Day 35) to the recovered subject. If the gouty arthritis does not disappear by 1 week or shorter after the specified visit day (ie, within Day 35), the subject is to be discontinued from the study treatment.
- d: Subjects who have developed gouty arthritis that has not disappeared by Week 12, are to continue to take the current investigational product without increasing dose for up to 1 week after the specified visit date (ie, up to Day 91) until the event disappears, and following the resolution of event, the study drug with increasing dose is to be dispensed at an Unscheduled Visit (ie, before or on Day 91) to the recovered subject. If the gouty arthritis does not disappear by 1 week or shorter after the specified visit day (ie, within Day 91), the subject is to be discontinued from the study treatment.
- e: Subjects who have developed gouty arthritis that has not disappeared by Week 24, are to continue to take the investigational product for up to 1 week after the specified visit date (ie, up to Day 175) until the event disappears. After then, regardless of outcome of the gouty arthritis, the subjects are to undergo all procedures/assessments scheduled at Week 24.
- f: If a subject meets any of the criteria: 1) a history of urinary calculi; 2) a urine pH of <6.0 on clinical examination after obtaining consent, urine alkalinizer (citrate preparations, et al) must be coadministered. Even if a subject meets none of the criteria, urine alkalinizer (citrate preparations, et al) is to be coadministered as needed.
- g: Physical examinations will only be performed at Visit 1, Visit 5, Visit 8, and at Early Termination Visit. For all other visits during the study, the physical examinations will only be performed when there is a complaint from the subject. Clinically significant abnormal findings from the physical examinations will be reported as adverse events.
- h: Vital signs include systolic and diastolic blood pressure, pulse, and temperature.
- i: Height without shoes will be measured.
- j: Clinical laboratory tests include hematology, blood chemistry, and urinalysis.
- k: Viral screening for hepatitis B (HBsAg), hepatitis C (HCV antibody IgG), and HIV will be conducted.
- l: The baseline is to be selected between 14 days and 4 day before, whichever is closer to the randomization day.
- m: Female subjects only.
- n: If subject has a normal ECG baseline reading, but during any visit thereafter the QTcF is measured as >450 ms, 3 consecutive ECGs, including the initial ECG with QTcF >450 ms, separated by at least 5 minutes will be performed to confirm the abnormality. ECG interpretation (categorized as normal; abnormal, not clinically significant; and abnormal, clinically significant) and parameters (QTcF, QT, PR, QRS, RR and heart rate) will be recorded on the CRF.
- o: At the unscheduled visit, as for the 2 safety assessments (ie, lab tests and ECG) and SUA assessment, they will be performed only if the investigator(s) judges as necessary based on the subject's condition.
- p: Height, weight, SUA level, urinary uric acid level, serum creatinine level, urinary creatinine level, and 60-minute urine volume will be measured.

### 9.5.3 Appropriateness of Measurements

All clinical assessments are standard measurements commonly used in studies of gout.

The safety assessments to be performed in this study, including hematology analyses, blood chemistry tests, urinalysis, radiologic studies, and assessment of AEs, are standard evaluations to ensure subject safety.

As stated in [Section 9.5.1.2.1](#), SUA level is considered a measure for the efficacy assessment and is not to be used in the safety assessment because there is expected to be variation in SUA level due to the pharmacological effects of dotinurad and febuxostat.

### 9.5.4 Reporting of Serious Adverse Events, Pregnancy, and Events Associated with Special Situations

#### 9.5.4.1 Reporting of Serious Adverse Events

**All SERIOUS ADVERSE EVENTS, regardless of their relationship to study treatment, must be reported to the designated CRO on a completed SAE form by email or fax as soon as possible but no later than 24 hours from the date the investigator becomes aware of the event.**

Serious adverse events, regardless of causality assessment, must be collected beginning from the time the subject signs the study ICF through the last visit and for 28 days after the subject's last dose. All SAEs must be followed to resolution or, if resolution is unlikely, to stabilization. Any SAE judged by the investigator to be related to the study treatment or any protocol-required procedure should be reported to the sponsor regardless of the length of time that has passed since study completion.

The detailed contact information for reporting of SAEs is provided in the Investigator Study File.

**For urgent safety issues**, please ensure all appropriate medical care is administered to the subject and contact the appropriate study team member listed in the Investigator Study File.

It is very important that the SAE report form be filled out as completely as possible at the time of the initial report. This includes the investigator's assessment of causality.

Any follow-up information received on SAEs should be forwarded within 1 business day of its receipt. If the follow-up information changes the investigator's assessment of causality, this should also be noted on the follow-up SAE form.

Preliminary SAE reports should be followed as soon as possible by detailed descriptions including copies of hospital case reports, autopsy reports, and other documents requested by the sponsor.

Reporting of AEs to regulatory authorities are provided in [Section 9.5.4.6](#).

#### 9.5.4.2 Reporting of Pregnancy and Exposure to Study Drug Through Breastfeeding

Any pregnancy in a female subject in which the estimated date of conception is either before the last visit or within 28 days of last study treatment, or any exposure to study drug through breastfeeding during study treatment or within 28 days of last study treatment, must be reported.

If an adverse outcome of a pregnancy is suspected to be related to study drug exposure, this should be reported regardless of the length of time that has passed since the exposure to study treatment.

A congenital anomaly, death during perinatal period, a spontaneous abortion or an induced abortion done due to safety concerns for either mother or fetus are considered to be an SAE and should be reported in the same time frame and in the same format as all other SAEs (see Reporting of Serious Adverse Events [[Section 9.5.4.1](#)]).

Pregnancies or exposure to study drug through breastfeeding must be reported by fax or email as soon as possible but no later than 24 hours from the date the investigator becomes aware of the pregnancy. The contact information for the reporting of pregnancies and exposure to study drug through breastfeeding is provided in the Investigator Study File. The Pregnancy Report Form must be used for reporting. All pregnancies must be followed to outcome. The outcome of the pregnancy must be reported as soon as possible but no later than 24 hours from the date the investigator becomes aware of the outcome.

A subject who becomes pregnant must be withdrawn from the study.

#### 9.5.4.3 Reporting of Events Associated with Special Situations

##### 9.5.4.3.1 REPORTING OF ADVERSE EVENTS ASSOCIATED WITH STUDY DRUG OVERDOSE, MISUSE, ABUSE, OR MEDICATION ERROR

Adverse events associated with study drug overdose, misuse, abuse, and medication error refer to AEs associated with uses of the study drug outside of that specified by the protocol. Overdose, misuse, abuse, and medication error are defined as follows:

Overdose	Accidental or intentional use of the study drug in an amount higher than the protocol-defined dose
Misuse	Intentional and inappropriate use of study drug not in accordance with the protocol
Abuse	Sporadic or persistent intentional excessive use of study drug accompanied by harmful physical or psychological effects

---

Medication error	Any unintentional event that causes or leads to inappropriate study drug use or subject harm while the study drug is in the control of site personnel or the subject.
	All AEs associated with overdose, misuse, abuse, or medication error should be captured on the Adverse Event CRF and also reported using the procedures detailed in Reporting of Serious Adverse Events ( Section 9.5.4.1 ) even if the AEs do not meet serious criteria. Abuse and Intentional Overdose, even if asymptomatic, are always to be captured as an AE. If the AE associated with an overdose, misuse, abuse, or medication error does not meet serious criteria, it must still be reported using the SAE form and in an expedited manner but should be noted as nonserious on the SAE form and the Adverse Event CRF.

#### 9.5.4.3.2 REPORTING OF ABNORMAL HEPATIC TESTS OF CLINICAL INTEREST

The following combination of abnormal laboratory tests\*, as determined by way of protocol-specified laboratory testing or unscheduled laboratory testing and whether nonserious or serious, should be entered on the Adverse Event CRF and reported using the procedures detailed in Reporting of Serious Adverse Events ([Section 9.5.4.1](#)). If the event does not meet serious criteria, the seriousness criteria on the SAE form should be indicated as “nonserious.”

- Elevated AST or ALT lab value that is greater than or equal to  $3 \times$  ULN  
AND
- Elevated total bilirubin lab value that is greater than or equal to  $2 \times$  ULN  
AND AT THE SAME TIME
- Alkaline phosphatase lab value that is less than  $2 \times$  ULN

\*Note: These criteria are based upon available regulatory guidance documents. The purpose of the criteria is to specify a threshold of abnormal hepatic tests that may require additional evaluation for an underlying etiology. In addition to reporting the abnormal hepatic laboratory tests on an SAE form, the site should also consult the medical monitor for guidance on assessment and follow-up. At a minimum, laboratory testing should be repeated at least once weekly until improvement or identification of a cause unrelated to study drug use that is unlikely to improve.

#### 9.5.4.4 Expedited Reporting

The sponsor must inform investigators and regulatory authorities of reportable events, in compliance with applicable regulatory requirements, on an expedited basis (ie, within specific time frames). For this reason, it is imperative that sites provide complete SAE information in the manner described above.

#### 9.5.4.5 Breaking the Blind

In the case of a medical emergency where the appropriate treatment of the subject requires knowledge of the study treatment given, the investigator may break the randomization code for an individual subject. In all such cases, the AE necessitating the emergency blind break

will be handled as an SAE in accordance with the procedures indicated above. Any broken code will be clearly justified and documented. The medical monitor must be notified immediately of the blind break.

#### 9.5.4.6 Regulatory Reporting of Adverse Events

Adverse events will be reported by the sponsor or a third party acting on behalf of the sponsor to regulatory authorities in compliance with local and regional law and established guidance. The format of these reports will be dictated by the local and regional requirements.

For this study, the Reference Safety Information which the Sponsor will use to assess expectedness is the Investigator Brochure of dotinurad/the approved China Package Insert of febuxostat.

#### 9.5.5 Completion/Discontinuation of Subjects

A subject may elect to discontinue the study at any time for any reason. Wherever possible, all subjects who discontinue the study are to complete the study's early discontinuation procedures indicated in the Schedule of Procedures/Assessments ([Table 3](#)).

Subjects who meet any of the following criteria will be discontinued from the study:

1. Subjects who withdrew consent
2. Subject choice (eg, change in residence)
3. Subjects who had AEs leading to discontinuation from the study
4. Subjects who were considered impossible to continue the study due to progression of gout or inadequate therapeutic effect of the study drug by the investigator
5. Subjects who take prohibited concomitant drugs during the study, and the use is considered to interfere with the efficacy assessments and affect the subject's safety by the investigator, following consultation with the sponsor
6. Subjects who change the dosage and/or administration, or initiate any restricted concomitant drugs during the study, and the change or initiation is considered to interfere with the efficacy assessments and affect the subject's safety by the investigator, following consultation with the sponsor
7. Subjects who begin to routinely receive NSAIDs or corticosteroids (not including topical application) for a disease other than gouty arthritis
8. Subjects who developed gouty arthritis attack after the randomization day and before taking the first study drug
9. Subjects who developed gouty arthritis at Week 4 or 12, and the gouty arthritis did not disappear within 1 week after the specified visit date of Week 4 or 12
10. Subjects who developed nephrolithiasis (including clinical urinary calculi) after the first study treatment (excluding at the final visit)

11. Subjects who developed acute kidney injury (AKI) after the first study treatment (excluding at the final visit)

AKI is defined as any of the following (Kidney Disease: Improving Global Outcomes [KDIGO] 2012):

- Increase in serum creatinine (SCr) by  $\geq 0.3$  mg/dL ( $\geq 26.5$   $\mu$ mol/L) within 48 hours; or
- Increase in SCr to  $\geq 1.5$  times baseline, which is known or presumed to have occurred within the prior 7 days; or
- Urine volume  $<0.5$  mL/kg/h for 6 hours

12. Subjects with SUA level of  $\leq 2.0$  mg/dL for 2 consecutive visits (excluding at the final visit)

13. Subjects with AST or ALT level of  $5 \times$  ULN (excluding at the final visit)

14. Subjects with serum creatinine level of  $\geq 3.0$  mg/dL (excluding at the final visit)

15. Subjects who became pregnant after the first study treatment

16. Subjects who were considered inappropriate to continue the study due to any other reason by the investigator

Subjects who discontinue early from the study will be discontinued for 1 primary reason of the above reasons. In addition to the primary reason, the subject may indicate 1 or more secondary reason(s) for discontinuation. Study disposition information will be collected on the Subject Disposition CRF.

The investigator will promptly explain to the subject involved that the study will be discontinued for that subject and provide appropriate medical treatment and other necessary measures for the subject. A subject who has ceased to return for visits will be followed up by mail, phone, or other means to gather information such as the reason for failure to return, the status of treatment compliance, the presence or absence of AEs, and clinical courses of signs and symptoms.

A subject removed from the study for any reason may not be replaced. In some circumstances, a subject who fails in the Screening Phase may be rescreened once following consultation with Medical Monitor of the Sponsor. Any such subject will be assigned a new subject identification number.

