#### 9.1.3 Treatment II Phase

The duration of Treatment II Phase is from the first day after Week 4 to the last day of Week 24/Early Termination Visit. During the Treatment II Phase, subjects in the dotinurad group will take dotinurad 2 mg/day once daily for 8 weeks initially and 4 mg/day once daily for 12 weeks. Subjects in the febuxostat group will take febuxostat 40 mg/day once daily for 20 weeks.

Vital signs, concomitant therapy, safety assessments (including gouty arthritis, urinary calculi, acute renal failure, liver injury), blood and urine for standard clinical laboratory assessments will be collected at each visit of Treatment II Phase. Physical examination and 12 lead ECG will be collected at Visit 5 and Visit 8. Serum  $\beta$ -hCG (or hCG) test, abdominal ultrasound and abdominal radiography will be collected at Visit 8. And SUA level will be assess at each visit. As for the details, see [Table 3](#).

If a subject has any symptoms, signs, or findings about urinary calculi, acute renal failure, and severe liver injury during the whole Treatment Phase, the subject needs to have an unscheduled visit to assess the related situation.

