highest severity will be used in the calculation of the incidence of TEAE within that preferred term (SOC) by severity. If a subject experiences more than one TEAE within a preferred term (or SOC), the occurrence considered most closely related to study drug will be used in the calculation of the incidence of TEAE with that preferred term (SOC) by relationship (given by investigator).

In addition, the following TEAEs of interest will be summarized by PT and treatment group.

- Urinary calculi defined by MedDRA HLGT “Urolithiases”
- Liver injury defined by MedDRA SMQ “Hepatic disorders”
- Acute renal failure defined by MedDRA SMQ “Acute renal failure”

TEAEs for the following subgroups will be summarized by SOC, PT and treatment group:

- SUA level category (<9; 9 to <10; 10 to <11;  $\geq$ 11 mg/dL)
- BMI category (<25;  $\geq$ 25 kg/m^2)
- Classification of hyperuricemia (overproduction type, underexcretion type, combined type, other type)

A subject data listing of all AEs, all AEs leading to death, all SAEs and all AEs leading to discontinuation from study drug will be provided.

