#### 4.6.3 Laboratory Values

Laboratory results will be summarized using Système International (SI) units, as appropriate. For all quantitative parameters listed in protocol Section 9.5.1.4.4, the actual value and the change from baseline to each postbaseline visit will be summarized by visit and treatment group using descriptive statistics. Qualitative parameters listed in protocol Section 9.5.1.4.4 will be summarized using frequencies (number and percentage of subjects), and changes from baseline to each postbaseline visit will be reported using shift tables. Percentages will be based on the number of subjects with both nonmissing baseline and relevant postbaseline results.

Laboratory test results will be assigned a low/normal/high (LNH) classification according to whether the value was below (L), within (N), or above (H) the laboratory parameter's reference range. Within-treatment comparisons for each laboratory parameter will be based on 3-by-3 tables (shift tables) that compare the baseline LNH classification to the LNH classification at each postbaseline visit. Similar shift tables will also compare the baseline LNH classification to the LNH classification for the highest and lowest value.

[Appendix 1](#) (Sponsor's Grading for Laboratory Values) presents the criteria that will be used to identify subjects with treatment-emergent markedly abnormal laboratory values (TEMAVs). A TEMA V is defined as a postbaseline value with an increase from baseline to a grade of 2 or higher. When displaying the incidence of TEMA Vs, each subject may be counted once in the laboratory parameter high and in the laboratory parameter low categories, as applicable.

The number (percentage) of subjects with TEMA V (markedly abnormal high/low) will be summarized by treatment group.

The number (percentage) of subjects who met the following criteria for the hepatic test at the same time will be summarized by treatment group. If a subject met the criteria more than once for available laboratory data, the subject will be counted only once in the calculation of the incidence.

- Elevated AST or ALT lab value that is greater than or equal to  $3 \times$  ULN
- Elevated total bilirubin lab value that is greater than or equal to  $2 \times$  ULN
- Alkaline phosphatase lab value that is less than  $2 \times$  ULN

A subject data listing of laboratory values will be provided.

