Bilirubin (hyperbilirubinemia)	>ULN – 1.5×ULN if baseline was normal; 1.0 – 1.5×baseline if baseline was abnormal	>1.5 – 3.0×ULN if baseline was normal; >1.5 – 3.0×baseline if baseline was abnormal	>3.0 – 10.0×ULN if baseline was normal; >3.0 – 10.0×baseline if baseline was abnormal	>10.0×ULN if baseline was normal; >10.0×baseline if baseline was abnormal
Calcium, serum-low (hypocalcemia)	<LLN – 8.0 mg/dL <LLN – 2.0 mmol/L Ionized calcium <LLN – 1.0 mmol/L	<8.0 – 7.0 mg/dL <2.0 – 1.75 mmol/L Ionized calcium <1.0 – 0.9 mmol/L	<7.0 – 6.0 mg/dL <1.75 – 1.5 mmol/L Ionized calcium <0.9 – 0.8 mmol/L	<6.0 mg/dL <1.5 mmol/L Ionized calcium <0.8 mmol/L
Calcium, serum-high (hypercalcemia)	>ULN – 11.5 mg/dL >ULN – 2.9 mmol/L Ionized calcium >ULN – 1.5 mmol/L	>11.5 – 12.5 mg/dL >2.9 – 3.1 mmol/L Ionized calcium >1.5 – 1.6 mmol/L	>12.5 – 13.5 mg/dL >3.1 – 3.4 mmol/L Ionized calcium >1.6 – 1.8 mmol/L	>13.5 mg/dL >3.4 mmol/L Ionized calcium >1.8 mmol/L
Creatinine	>ULN – 1.5×ULN	>1.5 – 3.0×baseline; >1.5 – 3.0×ULN	>3.0×baseline; >3.0 – 6.0×ULN	>6.0×ULN

	Grade 1	Grade 2	Grade 3	Grade 4
GGT ( $\gamma$ -glutamyl transpeptidase)	>ULN – 2.5 $\times$ ULN if baseline was normal; 2.0 - 2.5 $\times$ baseline if baseline was abnormal	>2.5 – 5.0 $\times$ ULN if baseline was normal; >2.5 - 5.0 $\times$ baseline if baseline was abnormal	>5.0 – 20.0 $\times$ ULN if baseline was normal; >5.0 - 20.0 $\times$ baseline if baseline was abnormal	>20.0 $\times$ ULN if baseline was normal; >20.0 $\times$ baseline if baseline was abnormal
Glucose, serum-low (hypoglycemia)	<LLN – 55 mg/dL <LLN – 3.0 mmol/L	<55 – 40 mg/dL <3.0 – 2.2 mmol/L	<40 – 30 mg/dL <2.2 – 1.7 mmol/L	<30 mg/dL <1.7 mmol/L
Potassium, serum-high (hyperkalemia)	>ULN – 5.5 mmol/L	>5.5 – 6.0 mmol/L	>6.0 – 7.0 mmol/L	>7.0 mmol/L
Potassium, serum-low (hypokalemia)	<LLN – 3.0 mmol/L		<3.0 – 2.5 mmol/L	<2.5 mmol/L
Sodium, serum-high (hypernatremia)	>ULN – 150 mmol/L	>150 – 155 mmol/L	>155 – 160 mmol/L	>160 mmol/L
Sodium, serum-low (hyponatremia)	<LLN – 130 mmol/L	125-129 mmol/L	120-124 mmol/L	<120 mmol/L

	Grade 1	Grade 2	Grade 3	Grade 4
Triglyceride, serum-high (hypertriglyceridemia)	150 – 300 mg/dL 1.71 – 3.42 mmol/L	>300 – 500 mg/dL >3.42 – 5.7 mmol/L	>500 – 1000 mg/dL >5.7 – 11.4 mmol/L	>1000 mg/dL >11.4 mmol/L

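### The 4-weekly visits cannot time the AKI criteria, no rule says when a rise is presumed recent, and the TEMAV rule misses creatinine rises of 1.5-fold to just under 2-fold in subjects entering at >1.5 to 2.0×ULN

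*Protocol*

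**What the plan says.** **AKI rule.** Criterion 11 in protocol section 9.5.5 requires withdrawal for AKI after the first dose, except at the final visit. Any one of three limbs is enough:

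- a creatinine rise of at least 0.3 mg/dL "within 48 hours; or"
- a creatinine of at least 1.5 "times baseline, which is known or presumed to have occurred within the prior 7 days"
- urine volume below 0.5 "mL/kg/h for 6 hours"

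Criterion 14 separately withdraws "Subjects with serum creatinine level of" 3.0 mg/dL or more, again except at the final visit.

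**Schedule.** Protocol section 9.1.3 says that "blood and urine for standard clinical laboratory assessments will be collected at each visit of Treatment II Phase". Table 3 places the laboratory tests, which include creatinine, at Screening, Weeks 4, 8, 12, 16, 20 and 24, and early termination. The only timed urine volume is a 60-minute collection at Screening (section 9.5.1.1.3).

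**Reporting.** Acute renal failure must always be reported as an adverse event (protocol section 9.5.1.4.3). SAP section 4.6.2 summarises "Acute renal failure defined by MedDRA SMQ" as an event of interest. For laboratory values, SAP section 4.6.3 states that a TEMAV "is defined as a postbaseline value with an increase from baseline to a grade of 2 or higher". SAP Appendix 1 gives creatinine Grade 2 as ">1.5 – 3.0×baseline; >1.5 – 3.0×ULN". Grade 3 is above 3.0×baseline, or above 3.0 and up to 6.0×ULN.

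**The concern.** Acute renal failure is one of four study-specific events in a trial of a drug that acts on the renal tubule, so its count by arm matters.

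The AKI limbs are defined over hours or days, while planned sampling is spaced in weeks. Two sites seeing the same Week 16 creatinine could reasonably classify it differently. The acute renal failure table counts reported events and so inherits that difference.

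The laboratory summary does not depend on site judgement, but it has a gap of its own. A subject who starts at Grade 2 on the ULN limb cannot rise to Grade 2. Some proportional rises that would be flagged from a better baseline are therefore not flagged from a worse one.

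**Working it through.** The plan gives no figure of its own on this point. The check is arithmetic on the visit windows and the grading table.

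**1. Can scheduled samples time the AKI limbs?** The smallest gap is the start of the next window minus the end of the previous one (Table 3).

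| Pair | Smallest gap (days) |
|---|---|
| Screening to Week 4 | 23 − (−4) = 27 |
| Week 4 to 8 | 51 − 33 = 18 |
| Week 8 to 12 | 77 − 61 = 16 |
| Week 12 to 16 | 105 − 91 = 14 |
| Week 16 to 20 | 133 − 119 = 14 |
| Week 20 to 24 | 161 − 147 = 14 |

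No two scheduled samples can show a change within 48 hours, or one known to lie within 7 days. The urine-volume limb has no scheduled measurement. That leaves a 1.5-fold rise presumed recent, and neither document says how to presume.

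**2. Which rises does TEMAV miss?** Inputs are the creatinine grades in SAP Appendix 1 and three reading assumptions:

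- Baseline is graded on the ULN limb only.
- The post-baseline grade is the worse of the two limbs.
- A TEMAV needs a higher grade than at baseline.

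The third assumption is supported by SAP section 7, which assigns grade 0 to a missing baseline when TEMAVs are determined. That rule has a use only if grades are compared.

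Let b be the baseline in multiples of ULN, above 1.5 and below 3.0. The subject starts at Grade 2 and is flagged only above 3×ULN, that is, at a fold rise above 3/b. The 3×baseline limit lies higher still, because b exceeds 1.

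| b (×ULN) | Flagged above fold 3/b | 1.5-fold rise reaches (×ULN) | Flagged? | 2-fold rise reaches (×ULN) | Flagged? |
|---|---|---|---|---|---|
| 1.51 | 1.99 | 2.27 | no | 3.02 | yes |
| 1.6 | 1.88 | 2.40 | no | 3.20 | yes |
| 1.8 | 1.67 | 2.70 | no | 3.60 | yes |
| 2.0 | 1.50 | 3.00 | no | 4.00 | yes |
| 2.2 | 1.36 | 3.30 | yes | 4.40 | yes |
| 2.5 | 1.20 | 3.75 | yes | 5.00 | yes |

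By contrast, a 1.5-fold rise from 1.2×ULN goes from Grade 1 to Grade 2 (1.8×ULN) and is flagged. The gap is therefore baselines of >1.5 to 2.0×ULN and rises from 1.5-fold up to 3/b.

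**3. Example in mg/dL.** The documents give no ULN; assume 1.2 mg/dL. Baseline 1.9 is 1.9/1.2 = 1.58×ULN, Grade 2. A value of 3.0 is 3.0/1.9 = 1.58×baseline and 3.0/1.2 = 2.5×ULN, still Grade 2. This meets criterion 14 and the size (not the timing) of the 1.5-fold limb, yet it is not a TEMAV. The flag would come above 3 × 1.2 = 3.6 mg/dL.

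**4. Overlap with criterion 14.** A 1.5-fold rise reaches 3.0 mg/dL from any baseline of at least 3.0/1.5 = 2.0 mg/dL. In multiples of ULN that is 2.0 at ULN 1.0, 1.67 at ULN 1.2 and 1.43 at ULN 1.4. The band that escapes both rules for a 1.5-fold rise is about 1.5–2.0×ULN, 1.5–1.67×ULN and none, respectively.

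**5. Rises of 0.3 mg/dL.** From above 1.5×ULN these are flagged only when they cross 3×ULN: from above 2.7 mg/dL at ULN 1.0, or above 3.3 mg/dL at ULN 1.2. Below 1.5×ULN, at ULN 1.2, they are flagged only from baselines under 0.6 mg/dL or from just above 1.5 to 1.8 mg/dL. This limitation is not specific to subjects with a high baseline.

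**The case against.** The other side has substantial points.

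- **Criterion 11 is not self-contradictory.** It applies to AKI however discovered, and its second limb expressly allows a presumption from a single value. A reader might infer that the rule can never be met on this schedule; the documents do not support that. Section 9.1.3 also requires an unscheduled visit for symptoms, signs or findings of acute renal failure. This is only a partial remedy. Laboratory tests at that visit are at the investigator's discretion (Table 3, note o), and a later repeat cannot date a rise that arose between visits weeks apart.
- **TEMAV is not blind to everyone entering above 1.5×ULN.** A reader might infer that it is. In fact every 2-fold rise from above 1.5×ULN is flagged, and so is every 1.5-fold rise from above 2.0×ULN. The subjects with the highest baselines are not the ones missed.
- **The TEMAV definition has another reading.** If it means any increase in value that lands in Grade 2 or higher, every case above is flagged. The grade 0 rule makes this less likely but does not exclude it.
- **Other outputs exist.** Discontinuation reasons are tabulated by arm (protocol section 9.7.1.3, SAP section 4.2.2), so a criterion 14 withdrawal should appear there. Creatinine change is summarised by visit with its maximum, and values are listed. However, a count under criterion 11 carries the same site judgement, and both criteria exempt the final visit, which closes the 4 mg period. The low/normal/high shift tables show these subjects as High to High. Mean changes do not count individuals.

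**Conclusion.** The point stands, with two limited parts.

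1. The schedule cannot time the AKI limbs, and there is no rule for the presumption. Reported AKI and the acute renal failure table therefore depend partly on site judgement. Unscheduled visits and discontinuation reasons only partly offset this.
2. On the grade-increase reading, TEMAV misses creatinine rises of 1.5-fold to just under 2-fold that stay at or below 3×ULN, in subjects entering at >1.5 to 2.0×ULN.

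A reader may want a number of subjects. The documents give neither the creatinine ULN nor the eGFR formula, so any count would rest on an assumed share of high baselines. It would also overstate the problem unless limited to those who then had a missed rise. Entry at eGFR 30 or above does not exclude such baselines, but exclusion 11 (clinically significant renal disease) narrows them. The number is probably small.

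The primary efficacy test is not in question. This is a gap in safety reporting that is cheap to close.

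**What to change.** **SAP section 4.6.3.** Add one table by treatment group from creatinine already collected, final visit included and regardless of baseline grade. Give the number and percentage of subjects with:

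- a largest post-baseline value of at least 1.5, 2 and 3 times baseline
- any post-baseline value of at least 3.0 mg/dL

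A rise of at least 0.3 mg/dL may be shown descriptively. It should not be labelled AKI, because the 48-hour limit is not observed.

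**Protocol section 9.5.5.** Criterion 11 and the 4-weekly schedule in Table 3 must be reconciled so that all sites read a scheduled-visit rise in the same way. The clinical content is for the sponsor to decide.

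**Cost.** One extra descriptive safety table and a protocol clarification. The table needs no new samples.
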